Number of Trial Centers	Up to 25 US trial centers with a specialty in pediatric burn care will participate. No center will contribute more than 25% of the total randomized subjects without written Sponsor permission.
Duration of Participation	Each subject will participate in the trial for 52 weeks post-treatment.
Primary Effectiveness Endpoint	The primary effectiveness endpoint is incidence of Index Burns with Day 10 healing post-treatment, evaluated by an observer blinded to treatment allocation, with confirmation at Day 28. If the Index Burn undergoes a secondary surgical treatment for closure (including conventional autografting) prior to the Day 28 visit, this will be considered an endpoint failure.
	The hypothesis to be evaluated is whether the incidence of Day 10 healing post- treatment is greater (superior) with RECELL treatment vs. Control treatment.
Safety Endpoints	Safety will be evaluated in terms of treatment-related adverse events and serious device-related adverse events.
Secondary Effectiveness Endpoints	 Specific secondary endpoints to be investigated for potential labeling claims include the following: 1. Incidence of Index Burn Day 21 post-treatment healing (confirmed on Day 28). 2. Percent area of Index Burn requiring autografting. 3. Incidence of conventional autografting to achieve Index Burn healing. Each endpoint will be tested in a fixed hierarchical method at a one-sided 0.025 significance level in the above order. These secondary endpoints/hypotheses will only be evaluated if the null hypothesis for the primary endpoint is rejected in the appropriate direction, and each secondary endpoint will only be evaluated if the null hypothesis of equality, for the endpoint preceding it in the list above, is rejected in the appropriate direction.
Tertiary Endpoints/ Data Collection	 the appropriate direction. Absolute area (cm²) of Index Burn requiring autografting. Index Burn pain scores at dressing changes assessed by the health care provider performing the dressing change using the Face, Legs, Activity, Cry, Consolability (FLACC) Scale. Subject reported Index Burn pain scores at dressing changes. Percent epithelialization of the Index Burn per digital planimetry. Index Burn POSAS scar ratings. BOQ Outcomes (raw scores and recovery curves for all domains), with baseline at Day 10.

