Statistical Considerations	documented. Based on medical input, the estimated proportion of subjects with confirmed day 10 healing is anticipated to be approximately 75% for the Control group. It is estimated that the proportion of RECELL subjects with confirmed day 10 healing will be 92.5%. Assuming power of 80%, using a one-sided z-test of proportions and one-sided alpha of 0.025 requires 69 subjects per group (138 subjects total). The total sample size has been increased by 12% to 160 subjects to adjust for missing data.
	The hypothesis to be evaluated is whether the incidence of Day 10 healing post- treatment (confirmed at Day 28 post-treatment) is greater (superior) with RECELL treatment vs. Control treatment.
	A formal unblinded interim analysis comparing treatments on the primary endpoint will be conducted once 50% of total enrollment has completed the primary effectiveness endpoint follow-up (i.e., 80 subjects have been randomized and reached the Day 28 healing confirmatory visit or would have reached the Day 28 visit had they not prematurely withdrawn).
	The unblinded interim analysis will be based on O'Brien-Fleming stopping rules. At the interim look, the one-sided p-value will need to be less than or equal to 0.00153 with results favoring RECELL in order to stop the study for reasons of overwhelming effectiveness of RECELL; the one-sided p-value will need to exceed 0.45604 to stop the study for futility. The one-sided p-value at the final analysis needs to be less than or equal to 0.02496, rather than the usual 0.025 required for a study without an interim analysis. This interim analysis will be based on patients with available primary endpoint data; there will no imputation of missing data at this interim analysis.
	The Intent to Treat (ITT) population will consist of all enrolled subjects who are randomized, with data analyzed according to randomized treatment assignment.
	The Modified Intent to Treat (mITT) Population will consist of all enrolled subjects who are randomized and treated, with data analyzed according to randomized treatment assignment. This population will be utilized as a primary analysis population for the primary and secondary effectiveness endpoints.
	Per Protocol (PP) Population will consist of mITT subjects who do not have major protocol deviations with data analyzed according to treatment received. This population will be utilized as a secondary analysis population for the primary and secondary effectiveness endpoints.

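### Labeling-claim secondaries carry a flat one-sided 0.025 in a two-look design, so the level for Day 21 healing is not guaranteed if they are tested at the look where the primary succeeds (minor)

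*Combined protocol and SAP*

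**What the plan says.** The Secondary Effectiveness Endpoints row of the synopsis lists three endpoints intended for possible labeling claims: Day 21 healing confirmed at Day 28, percent of the Index Burn autografted, and incidence of autografting. The level is given as: "Each endpoint will be tested in a fixed hierarchical method at a one-sided 0.025 significance level in the above order". The gate is: "These secondary endpoints/hypotheses will only be evaluated if the null hypothesis for the primary endpoint is rejected in the appropriate direction". Neither sentence names a look.

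The primary endpoint is "incidence of Index Burns with Day 10 healing post-treatment, evaluated by an observer blinded to treatment allocation, with confirmation at Day 28". Under Statistical Considerations it can succeed at two points. At the interim, "the one-sided p-value will need to be less than or equal to 0.00153 with results favoring RECELL"; otherwise, "The one-sided p-value at the final analysis needs to be less than or equal to 0.02496". The interim is described this way: "A formal unblinded interim analysis comparing treatments on the primary endpoint will be conducted once 50% of total enrollment" has completed follow-up, meaning 80 of 160 subjects. Under Trial Design, an early success stops enrollment. It does not end follow-up, since "Each subject will participate in the trial for 52 weeks post-treatment".

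The synopsis gives no secondary level per look, no data set for the secondaries after an early stop, and no named test for Day 21 healing. The z-test is mentioned only for sizing the primary.

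**The concern.** The hierarchy protects the secondaries while the primary null is true, because a false secondary claim then needs a false primary claim first. It does not protect them when RECELL speeds healing to Day 10 but leaves Day 21 healing unchanged. The gate then opens often, and the Day 10 data choose the look.

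Both endpoints are confirmed at Day 28, so a confirmed Day 10 healer would normally also count as a Day 21 healer, and the two test statistics are positively correlated. An interim sample that favors RECELL strongly enough at Day 10 to stop the trial will also tend to favor it at Day 21. Testing Day 21 healing on that sample at the full 0.025, with a second chance at 0.025 if the trial continues, can push the error above 0.025.

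At stake is a Day 21 labeling claim made at a level somewhat above the stated one, and a choice of data set and test left open until after unblinding.

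**Working it through.** **Inputs from the synopsis.** Day 10 healing 75% vs 92.5%; one-sided 0.025; power 80%; 69 per group; 160 enrolled; interim at 80; bounds 0.00153 (efficacy), 0.45604 (futility), 0.02496 (final).

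**Assumptions, not in the synopsis.** The same Day 21 rate q in both arms; every Day 10 healer is a Day 21 healer (nesting); pooled z-test for Day 21; no sample size increase.

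**1. The plan's own figures.** n = [1.960·√(2·0.8375·0.1625) + 0.842·√(0.75·0.25 + 0.925·0.075)]² / 0.175² = (1.023 + 0.427)² / 0.0306 ≈ 68.6, so 69 per group, as stated. O'Brien-Fleming-type spending at half information gives 2[1 − Φ(2.241/√0.5)] = 0.001525, matching 0.00153. With binding futility, a final level of 0.02496 gives a total of 0.0250. So the primary is adjusted for two looks.

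**2. General bound for a secondary.** With Z the primary statistic and S the secondary statistic at looks 1 and 2, the error is

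P(Z1 ≥ 2.962, S1 ≥ 1.96) + P(0.110 ≤ Z1 < 2.962, Z2 ≥ 1.961, S2 ≥ 1.96).

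This cannot exceed P(S1 ≥ 1.96 or S2 ≥ 1.96) with correlation √0.5 between looks, which is 0.0416. Maximized over the size of the primary effect, it is 0.0250, 0.0286, 0.0347 and 0.0407 at primary-secondary correlations of 0, 0.5, 0.9 and nearly 1.

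**3. Correlation under nesting.** Within an arm, the covariance per subject is p(1 − q). Hence ρ = (0.75 + 0.925)(1 − q) / √{[0.75·0.25 + 0.925·0.075]·2q(1 − q)}. For q = 0.925: 0.1256 / √(0.2569·0.1388) = 0.67. For q = 0.95 it is 0.54, and for q = 0.98 it is 0.33.

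**4. Simulated error at flat 0.025.** First figure: 40 then 80 evaluable per arm. In parentheses: 34 then 69. The columns differ in the subjects analysed after an early stop.

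| Day 21 rate | 80 interim subjects | 24 more | full sample |
|---|---|---|---|
| 92.5% | 0.034 (0.033) | 0.027 (0.033) | 0.022 (0.026) |
| 95% | 0.025 (0.024) | 0.024 (0.027) | 0.021 (0.024) |
| 98% | 0.012 (0.009) | 0.013 (0.010) | 0.015 (0.012) |

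The 24 extra subjects are an assumption, since the synopsis gives no enrollment rate. The full-sample column is in effect one fixed test; its 0.026 is discreteness of the z-test, not an effect of the two looks.

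**5. What drives the 0.034.** One ungated pooled z-test at 40 per arm and q = 92.5% already has error 0.029. With Fisher's exact test the error is at most 0.012 in every scenario. With a smaller Day 10 benefit (89% vs 75%, 80 interim subjects), the error is 0.036 at a Day 21 rate of 89% and 0.029 at 92.5%.

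**6. Rates among early stops, beside a valid test.** An early stop has probability 0.15-0.17. Among early stops (40 then 80 per arm), the flat test on the 80 interim subjects gives a false Day 21 claim in about 15%, 9% and 1% at q = 92.5%, 95% and 98%. A valid single 0.025 test on all 160 subjects gives about 9%, 6-7% and 3%.

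**7. Levels that hold.** Solving P(S1 ≥ c or S2 ≥ c) = 0.025 at half information gives c = 2.178, or 0.0147 at either look. With 0.00153 at the interim, the final level is 0.0245. Reusing the primary's 0.00153 and 0.02496 totals 0.0255 without credit for futility stopping.

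**The case against.** The strongest reply is that the synopsis never says the secondaries are tested on interim data. The interim comparison is limited to the primary, an early success stops enrollment only, and follow-up continues to Week 52. One later analysis of the secondaries is therefore also consistent with the text, and a fuller statistical section may already settle the matter. This stands. Testing at the look where the primary succeeds is a reading, and the point is conditional on it.

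The second reply is about size. The 92.5% case is a corner in which no RECELL burn heals between Day 10 and Day 21, and part of its 0.034 is small-sample behaviour of the z-test. At a 95% Day 21 rate with 80 interim subjects there is no clear excess, and at 98% the test is conservative. This also stands.

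A reader might infer from the 9-15% of false claims among early stops that the real error is several times 0.025. That does not follow. The rate given an early stop is not the error being controlled, and a valid single test also gives 6-9% there at Day 21 rates of 92.5-95%, because early stops are selected by correlated data.

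What the reply does not remove is that a level is stated, two looks are allowed, and nothing in the synopsis reconciles them.

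**Conclusion.** The concern holds in conditional form, and it is minor. If the secondaries are tested on the data of the look at which the primary succeeds, a flat 0.025 does not guarantee a 0.025 error for Day 21 healing when RECELL truly improves Day 10 healing but not Day 21 healing. The ceiling is about 0.042. At the planned Day 10 rates the error runs from about 0.012 to 0.034 with only the 80 interim subjects analysed, and there is no excess with all 160.

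A reader might go further and conclude that the plan breaches its level. The documents do not support that: they fix neither the look, the data set nor the Day 21 test, and several consistent choices keep the error at or below 0.025. The second and third secondaries sit behind further gates and were not simulated.

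The figures rest on nesting, assumed Day 21 rates, a pooled z-test and a fixed final size of 160. An increase toward 300 subjects was not modelled.

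**What to change.** In the SAP, before the interim:

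1. State that after an early stop the secondaries are tested once, on all subjects randomized by then, after their Day 28 follow-up.
2. Replace the flat 0.025 with a prespecified group sequential level for the look at which each secondary is tested. Examples are 0.0147 at either look, or 0.00153 at the interim and 0.0245 at the final. If another section already does this, cross-refer to it from the synopsis.
3. Name the test for Day 21 healing.
4. State that if the sample size is increased, the secondary level is protected by the same method as the primary. Fixed levels for an 80-of-300 split should not be quoted, because the increase depends on interim data.

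The change is to wording only. The secondary read-out after an early stop waits for Day 28 of subjects already randomized. The real cost is power. With assumed Day 21 rates of 81% vs 96% or 85% vs 98% and 24 extra subjects, overall secondary power is 0.74-0.82 at flat 0.025. It falls by about 3-4 points with 0.0147 at either look (to 0.70-0.78), or by 5-9 points with 0.00153 and 0.0245 (to 0.65-0.77). Both options are conservative at the planned effect, with error at most 0.018. Item 1 alone costs almost no power but does not by itself secure the level.

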Control Treatment	Mepilex [®] Ag Wound Dressing (Mölnlycke Health Care) is a standardly employed dressing for second-degree/partial-thickness burns due to its non-adherent and antimicrobial properties. The layered dressing includes a flexible, absorbent polyurethane foam pad embedded with silver sulfate compound and vapor permeable film backing with a silicone layer covered with a polyethylene release film.
Phase of Study	Pivotal Study
Proposed Indication for Use	The RECELL Device is indicated for treatment of partial-thickness burns in patients 1 year of age or greater.
Primary Objectives	To demonstrate that RECELL treatment of partial-thickness burn injuries, can safely and effectively increase the incidence of Day 10 healing compared with a standardized wound dressing. Also, the effects of both treatments on the incidence of conventional autografting, pain, itching, scarring, health-related quality of life and resource utilization will be investigated.
Planned Enrollment	To evaluate the primary endpoint, enrollment of 160 subjects is planned.
	This study utilizes an adaptive design with interim analysis for early stopping due to futility or positive outcome and, if necessary, sample size re-estimation in order to maintain adequate condition power. The maximum enrollment will be 300 subjects .
Trial Design	This is a prospective, parallel-arm, randomized (1:1), blinded evaluator, multicenter trial. Infants, children, and adolescents (aged from 1 through 16 years), male and female, with a burn injury that is no more than 30% of their total body surface area (TBSA) and no more than 10% TBSA is full-thickness burn injury, will be considered for participation.
	Randomization and assigned treatment must be performed within 72 hours of the burn injury for a subject to be treated within this study.
	Qualifying subjects will be randomized 1:1 either to treatment with RECELL or to Control (Mepilex [®] Ag Wound Dressing). Randomization will be stratified by investigational site and total burn area (<10% TBSA and \geq 10% TBSA). If there is more than one partial-thickness burn wound, the largest partial-thickness burn wound meeting eligibility requirements will be identified as the Index Burn (the burn wound that will be compared for effectiveness outcomes). The Index Burn will be a contiguous area at least 160 cm ² that excludes the face, hands, feet and genitalia.

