	 Investigator treatment preference. Health economics/medical resource utilization (determined using CRF data in conjunction with UB-04/CMS-1500 and/or similar hospital and physician claim forms for billing purposes to collect data associated with the initial hospital care and readmissions during follow-up as applicable). Index Burn Itch Man Scale ratings.
Pre-Randomization Inclusion Criteria	 Male or female patients aged 1 through 16 years (inclusive) with a partial-thickness thermal burn injury. The patient has a thermal burn injury that is: a. ≤ 30% TBSA (exclusive of superficial areas) and b. ≤ 10% TBSA is a full-thickness burn. The Index Burn must be a clean partial-thickness burn injury ≥160 cm² and between 2-20% BSA (inclusive). The Index Burn may not cover the face, hand, foot or the perineum/genitalia (Note: a patient with wounds in these areas may be enrolled but the Index Burn Area may not include these areas). The patient and/or parent/guardian agrees to comply with all compulsory study procedures and visit schedule. The patient and/or parent/guardian agrees to abstain from any other treatment for closure of the Index Burn for the duration of the study unless medically necessary. The patient and/or parent/guardian agrees to abstain from enrollment in any other interventional clinical trial for the duration of the study. In the opinion of the investigator, the patient and/or parent/guardian must be able to: understand the full nature and purpose of the study, including possible risks and adverse events, Understand instruction, and Provide voluntary informed written consent/assent as appropriate for

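### No covariate is named for the primary comparison; pre-specifying adjustment for Index Burn size would be a cheap efficiency gain, not the repair of an error.

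*Combined protocol and SAP*

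**What the plan says.** The Statistical Considerations section of the synopsis takes healing to be "anticipated to be approximately 75% for the Control group" and 92.5% with RECELL. It reaches 69 subjects per group for 80% power "using a one-sided z-test of proportions" and "one-sided alpha of 0.025", and enlarges the total from 138 to 160 for missing data. For the decision, "The one-sided p-value at the final analysis needs to be less than or equal to 0.02496"; the interim limits are 0.00153 for efficacy and 0.45604 for futility. The text available states no primary analysis model, no covariate and no handling of the stratification factors. It ends where Statistical Considerations restates the primary endpoint.

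The endpoint is healing of a single wound. Under the inclusion criteria that wound must be at least 160 cm² and "between 2-20% BSA (inclusive"). Under Trial Design, randomization is "stratified by investigational site and total burn area", the latter split at 10% TBSA. Index Burn size itself is not a stratification factor.

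**The concern.** Larger wounds plausibly take longer to close, so the size of the Index Burn is a natural candidate to predict Day 10 healing. It varies tenfold and has to be measured before randomization. A crude comparison of proportions makes no use of it. If size is prognostic, the crude test is less sensitive than it could be, and a chance difference in wound size between arms passes into the observed healing difference. The same statistic may drive early stopping on about 80 subjects and re-estimation of the sample size up to 300. An adjustment added after an imbalance has been seen would carry little weight, so the choice has to be made in advance.

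**Working it through.** **1. The plan's own figure.** Inputs from Statistical Considerations: 0.75, 0.925, one-sided 0.025, power 0.80. With pooled variance under the null and no continuity correction,

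n = [1.960 × √(2 × 0.8375 × 0.1625) + 0.842 × √(0.75 × 0.25 + 0.925 × 0.075)]² / 0.175² = 1.449² / 0.030625 = 68.6, so 69 per group.

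The figure reproduces. At 69 per group, power is 80.3% by the normal approximation and 82.0% by exact binomial enumeration. The crude test therefore delivers what the plan promises.

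**2. How far total burn area stands in for Index Burn size.** An Index Burn of 10% BSA or more must fall in the upper class, so stratification does balance size in part. Within classes much variation remains. The lower class can hold Index Burns from 2% to just under 10%. The upper class can hold 2% to 20%, because the total may also include up to 10% TBSA of full-thickness burn, wounds on excluded sites and smaller partial-thickness wounds. In simulation with log-uniform sizes, stratification cut the standard deviation of the between-arm difference in mean log2 size from about 0.165 to about 0.11, that is by about one third.

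**3. Power with and without adjustment.** The documents give no size effect and no size distribution, so both are assumptions. The first simulation used 69 per arm, 75% vs 92.5%, right-skewed sizes with mean 7% BSA, and 16,000 trials per row (Monte Carlo error about 0.3 points).

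| Odds ratio of healing per 5% BSA | Crude z | TBSA-stratified | Adjusted for size | Adjusted − crude | Adjusted − stratified |
|---|---|---|---|---|---|
| 1 (no effect) | 81.5% | 81.7% | 81.7% | 0.2 | 0.0 |
| 0.61 | 82.5% | 82.9% | 83.4% | 0.9 | 0.5 |
| 0.37 | 82.4% | 83.8% | 85.3% | 2.9 | 1.5 |
| 0.25 | 82.2% | 84.5% | 87.7% | 5.5 | 3.2 |

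The 0.2 in the first row is within simulation error.

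A second simulation put size on the log scale, with 138 subjects, limit 0.02496 and 3,000 trials per scenario (error about 0.7 points). Crude vs adjusted power, by odds ratio per doubling of size, with log-uniform sizes:
- 1.0: 82.3% vs 82.3%
- 0.8: 83.7% vs 84.1%
- 0.6: 81.2% vs 82.3%
- 0.45: 82.6% vs 84.9%
- 0.3: 82.7% vs 87.5%

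With sizes concentrated near 5% BSA the gains were smaller: 81.5% vs 82.0% at 0.6, and 82.5% vs 85.3% at 0.3. The two simulations agree in pattern.

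**4. Scale of chance imbalance.** At an odds ratio of 0.37 per 5% BSA, a 1% BSA difference in mean size moves the crude healing difference by about 2.8 points. The chance standard deviation of that difference in size is 0.44% BSA at 69 per arm, so a typical shift is 0.44 × 2.8 = 1.2 points. The standard error of the healing difference is √[(0.1875 + 0.0694)/69] = 6.1 points. At 40 per arm the size SD is 0.44 × √(69/40) = 0.58% BSA, a shift of 1.6 points against a standard error of √[(0.1875 + 0.0694)/40] = 8.0 points.

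**5. False-positive rate.** With no treatment effect and an odds ratio of 0.45 per doubling, the z-test rejected in 2.3% and the adjusted test in 2.5% of 6,000 trials under stratified allocation, against 2.496%. In the first set-up, at 80 per arm, the figures were 2.1–2.8% and 2.5–2.7%. At the interim (40 per arm, limit 0.153%) the adjusted test rejected in 0.09–0.18% of 40,000 trials. The simulation error there is about 0.02 points, so the upper value lies about 1.4 standard errors above the limit. Both tests are acceptable.

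**The case against.** A reader might infer three stronger claims, and the documents support none of them.

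- *The plan has committed to an unadjusted primary analysis.* The z-test appears in the sample-size sentence, which says what the 69 per group assumes. What can be said is that no model or covariate is stated in the text available.
- *Power is being lost.* That needs a size effect which the documents do not give. The larger gains need strong effects: over the 18-point size range, an odds ratio of 0.37 per 5% BSA multiplies the odds of healing by 0.37^3.6 = 0.028, a 36-fold fall, and 0.25 gives 0.25^3.6 = 0.0068, a 147-fold fall. In the second simulation, the strongest effect meant control healing of 95–97% at 2% BSA and 26–36% at 20%. In every scenario the crude test stays above 80%.
- *Chance imbalance in wound size invalidates the result.* Under randomization it is ordinary sampling error, which the test already covers; step 5 shows no inflation.

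Two further objections stand in part. Stratifying the test by total burn area alone recovers a little under half of the gain (0.4 of 0.9, 1.4 of 2.9 and 2.3 of 5.5 points), so the increment specific to Index Burn size is about 0.5 to 3 points. And adjustment is not quite free. At the interim about 4% of trials would have no RECELL failures (0.925^40 = 0.044), and an ordinary logistic fit for the standardized difference then breaks down. The score test itself is less exposed, because it fits only the model without treatment.

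What remains is that a baseline value the trial must collect is left unused, and that using it costs no power when it proves uninformative.

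**Conclusion.** The point holds as an efficiency recommendation. The unadjusted z-test is valid and meets the plan's stated power. Pre-specified adjustment for Index Burn size would add 0 points of power if size is not prognostic, about 1 point if the effect is moderate and about 3 to 6 points if it is strong.

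These figures rest on assumed size distributions, on an effect linear on the logit scale (in %BSA or in log size), and on the planned rates of 75% and 92.5%. Stratification by site was not represented in the second simulation. The adjusted model there held size alone, so a model that also carries total-burn-area class should be checked when the SAP is written. If a fuller analysis section names an adjusted model, the recommendation reduces to confirming that Index Burn size is in it.

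**What to change.** - **Primary test:** at both the interim and the final analysis, use a one-sided score test for treatment from a logistic model with Index Burn %BSA as a continuous covariate and total-burn-area class. Fix the linear or log scale in advance. The p-value limits stay as they are.
- **Adaptation:** base conditional power and sample-size re-estimation on the same statistic.
- **Estimate:** report the standardized risk difference from the model, which stays on the scale of the planned 75% vs 92.5%. State that the score test decides if its result and the interval disagree.
- **Fallback:** name in advance what replaces the ordinary fit if an arm has no failures, for example Firth penalization or a Mantel-Haenszel difference stratified by total burn area.
- **Sensitivity:** keep the unadjusted z-test.

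The cost is SAP wording, programming that includes the fallback and the re-estimation step, and a model-form choice that cannot be revisited after unblinding. No new data are needed, since Index Burn size is already required for eligibility. The sample size stays as it is.

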Standardized digital images of Index Burns taken during acute follow-up, including images taken the day the investigator made a decision to autograft will be presented, out of time sequence, to an Independent Medical Monitor (blinded to treatment allocation and investigator's determination) to review.
Longer-term follow-up visits will be performed at Weeks 8, 16, 24, 36 and 52 post- treatment (irrespective whether a subject had conventional autografting of the Index Burn).
At the Week 16, 24, 36 and 52 post-treatment visits, scar outcomes and disease- specific quality of life will be assessed. Scar outcomes will be measured using the Patient and Observer Scar Assessment Scale (POSAS) questionnaire, which includes components for both the Blinded Evaluator and the subject (or parent/guardian, as appropriate). Patient- and family-reported quality of life outcomes will be captured via the age-specific Burn Outcomes Questionnaire (BOQ). The BOQ evaluates several domains specific to longer-term burn outcomes including physical function, appearance, satisfaction and emotional health among others. Investigator treatment preference will be documented for each treating investigator, at each burn center, following the investigator's last subject's last visit.

	During the longer-term follow-up visits, the preferred method is in-person clinical visits, however (if necessary), these follow-up visits may be conducted remotely (e.g., via telemedicine) with the exception of the Week 52 visit. Treatment-related adverse events (e.g., infection, wound breakdown, etc.) are to be recorded for the Index and Non-Index Burn wounds as well as for donor sites. An interim analysis will be conducted after approximately 50% of total enrollment has reached the primary effectiveness endpoint (i.e., 80 subjects have completed the primary endpoint evaluation including confirmation of healing at Day 28). At that time, study enrollment may be discontinued due to futility or demonstration of effectiveness. If enrollment continues, a sample size re-estimation will be performed, and the sample size may be adjusted upwards to at most 300 subjects.
	A Data Monitoring Committee will be responsible for interim review of safety and effectiveness data and will be responsible for reviewing data from the interim and sample size re-estimation analyses.

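### The final threshold of 0.02496 keeps one-sided alpha at 0.025 only if the futility stop is binding, and the synopsis does not say that it is

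*Combined protocol and SAP*

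**What the plan says.** The Statistical Considerations row of the synopsis sets an overall one-sided alpha of 0.025 and one unblinded interim look at 50% of enrollment (80 of 160 subjects). On the boundaries it says "The unblinded interim analysis will be based on O'Brien-Fleming stopping rules". The interim effectiveness bound is one-sided p ≤ 0.00153. For futility, "the one-sided p-value will need to exceed 0.45604 to stop the study for futility". For the end of the trial, "The one-sided p-value at the final analysis needs to be less than or equal to 0.02496, rather than the usual 0.025".

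The Trial Design row describes what follows the look: "At that time, study enrollment may be discontinued due to futility or demonstration of effectiveness". It continues: "If enrollment continues, a sample size re-estimation will be performed, and the sample size may be adjusted upwards to at most 300 subjects". The supplied text calls the futility bound neither binding nor non-binding.

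**The concern.** A futility rule removes some trials that would otherwise have gone on to a false positive. If stopping is compulsory, the alpha saved in this way can be used to relax the final threshold. If stopping is optional, it cannot be used, because a trial that continues past the bound can still reject.

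The threshold 0.02496 takes this credit. The wording does not secure it: one passage says that enrollment may be discontinued, and the other gives the p-value needed in order to stop, which is a condition and not a duty.

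This threshold decides success on the primary endpoint, and the secondary endpoints intended for labeling are tested only if the primary null hypothesis is rejected. Nor is the bound remote. Under the null hypothesis the interim p-value exceeds 0.45604 in 1 − 0.45604 = 54.4% of trials, so its status should be settled before any unblinding.

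**Working it through.** **Inputs**, all from the Statistical Considerations row: overall one-sided alpha 0.025; information fraction t = 80/160 = 0.50; interim effectiveness p 0.00153 (z = 2.9616); interim futility p 0.45604 (z = 0.1104); final p 0.02496 (z = 1.9606).

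**Model.** Z1 and Z2 are the interim and final statistics, jointly normal under the null hypothesis with correlation √t. Sample size re-estimation is left out.

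**Step 1: reproduce the plan's figures.** O'Brien-Fleming-type (Lan-DeMets) spending at t = 0.5 gives 0.001525, which matches 0.00153. With futility binding,

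alpha = P(Z1 > 2.9616) + P(0.1104 < Z1 < 2.9616, Z2 > 1.9606) = 0.00153 + 0.02347 = 0.02500.

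Solving this equation for the final threshold returns 0.024960, the stated value.

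**Step 2: remove the futility credit.** If the bound is always overridden, the added term is

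P(Z1 < 0.1104, Z2 > 1.9606) = 0.000457,

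so alpha = 0.025000 + 0.000457 = 0.02546. Solving for the final threshold that restores 0.025 gives 0.024498 (z = 1.9686), not 0.02496. Classical O'Brien-Fleming bounds without futility (0.00258 and 0.0240) do not match either.

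**Step 3: where the excess comes from.** It arises from any final p ≤ 0.02496 after an override. Crossing the bound, continuing, and then landing between 0.0245 and 0.02496 has probability of only about 0.000016. The lower threshold therefore restores alpha mainly by rejecting slightly less often in trials that never crossed the bound.

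**Step 4: vary the information fraction.** This matters because "This interim analysis will be based on patients with available primary endpoint data".

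| t | alpha, always followed | alpha, always overridden | non-binding final threshold |
|---|---|---|---|
| 0.45 | 0.02483 | 0.02555 | 0.02440 |
| 0.50 | 0.02500 | 0.02546 | 0.02450 |
| 0.55 | 0.02510 | 0.02536 | 0.02459 |

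As an illustration, assume that 12% of the 80 interim subjects have no data, so that about 70 contribute. Against a final analysis of 160, t = 0.4375, the overridden alpha is 0.02558 and the non-binding threshold is 0.02437. Against 138, t is about 0.51.

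**Step 5: exact binomial check.** Assumed: pooled z-test, equal arms, no re-estimation. Overall alpha:

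| Per arm, interim then final | Null rate | 0.02496, followed | 0.02496, overridden | 0.02449, overridden |
|---|---|---|---|---|
| 40 then 80 | 70% | 0.02567 | 0.02613 | 0.02512 |
| 40 then 80 | 75% | 0.02585 | 0.02633 | 0.02506 |
| 40 then 80 | 80% | 0.02506 | 0.02553 | 0.02537 |
| 35 then 69 | 70% | 0.02545 | 0.02588 | 0.02588 |
| 35 then 69 | 75% | 0.02534 | 0.02578 | 0.02578 |
| 35 then 69 | 80% | 0.02514 | 0.02559 | 0.02559 |

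Overriding adds 0.00043 to 0.00048 in all six cases, in line with Step 2.

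**The case against.** The strongest reply is that the plan contains no error. The three thresholds agree with one another under a binding rule, and the match of 0.02496 is good evidence that a binding rule was meant. The text speaks of stopping rules and words effectiveness and futility alike. The word *may* covers both outcomes and can mean only that the result of the look is not yet known. No supplied passage gives anyone the power to override the bound. The supplied text is also only the synopsis, and a fuller statistical section could declare the bound binding. All of this stands. It shows that the intent is probably binding, but not that the supplied text says so.

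It also stands that the effect is small. The maximum requires every crossing to be overridden, and after a crossing under the null hypothesis the chance of a significant final result is 0.000457/0.544, about 0.08%. The excess is similar in size to the discreteness of the test: exact alpha is already above 0.025 in all six cases with futility followed, and at 35 then 69 per arm the lower threshold changes nothing.

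A reader might infer that 0.02496 was miscalculated, or that this trial's type I error is 0.0255. The documents support neither. The first fails because the value reproduces exactly under a binding stop. The second fails because 0.0255 is an upper limit for a design without re-estimation, whereas here any trial that continues goes on to re-estimation.

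**Conclusion.** The point holds as a mismatch between wording and threshold, and it is minor. The success criterion takes a futility credit that the supplied synopsis does not secure. At 50% information, overall one-sided alpha lies between 0.02500 (bound always followed) and about 0.0255 (bound always overridden). Over information fractions of 0.45 to 0.55 the overridden value runs from 0.02555 to 0.02536.

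These figures rest on the normal approximation, on the stated bounds taken as given, and on no sample size re-estimation. They do not show that anyone plans to override the bound, and they do not measure alpha after an increase toward 300 subjects.

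**What to change.** Preferred: state that the futility bound is non-binding and set the final one-sided threshold to about 0.0245 (0.02449 at exactly 50% information), recomputed at the actual interim information fraction. The recomputation is needed because a fixed 0.02449 with the bound always overridden gives 0.02509 at t = 0.45 and 0.02490 at t = 0.55. This makes type I error robust to either reading of the text under the normal approximation. It is not an exact guarantee, since discreteness can leave alpha slightly above 0.025.

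The cost is one sentence and one number. With 69 per group, 75% against 92.5% and futility followed, power falls from 81.4% to 81.2% (unpooled variance) or from 79.2% to 78.9% (pooled), about 0.2 percentage points. In the exact pooled test it does not visibly change: 86.7% at 80 per arm and 81.6% at 69 per arm, with either threshold.

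Alternative: keep 0.02496 and state in both synopsis rows that an interim p-value above 0.45604 is a binding stop. This costs no power but removes the freedom to continue past the bound.

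With either choice, alpha control after re-estimation must be specified separately.
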